Official Title: An Open Label, Proof-of-Principle, Pilot Study to Evaluate Pimavanserin
for the Treatment of Motor and Behavioral Symptoms of Tourette Syndrome.

NCT Number: Pending

Document date: 23FEB2021

Data at baseline and scheduled follow up visits per study protocol will be collected in the form of standardized rating scales used to measure symptom severity in Tourette syndrome as described below.

The primary endpoint is the change in the Total Tic Score (TTS) of the Yale Global Tic Severity Scale (YGTSS) from baseline to week 8 in TS patients treated with pimavanserin. The goal is to see if pimavanserin has an effect on this score. A reduction in score would indicate a clinical benefit and vice versa.

If this score is reduced from baseline to week 8 while taking the study drug, this will suggest clinical benefit. Any degree of reduction in this score will be described as a suggestion of clinical benefit. A similar approach will be applied to the other scales mentioned in the study protocol. If there is suggestion of clinical benefit, we will consider this an indication of feasibility for a larger study.

Secondary endpoints include changes from baseline to week 8 in: - Yale-Brown Obsessive Compulsive Scale (Y-BOCS) - Tourette Syndrome-Clinical Global Impression (TS-CGI) score - Tourette Syndrome-Patient Global Impression of Impact (TS-PGII) score - Gilles de la Tourette syndrome-quality of life scale (GTS-QOL) - Global Severity Score (GSS) of the YGTSS - Motor Tic Severity Score (MTSS) of the YGTSS - Vocal Tic Severity Score (VTSS) of the YGTSS - YGTSS Impairment score - Proportion of patients who have a reduction of 6 or more points in the TTS of the YGTSS - Proportion of patients who have a TS-CGI reduction of 2 or more points - Observed values and change in patient-assessed Tic-free Interval assessment.

All these variables will be analyzed over the 8 week treatment period. The data will be analyzed using standardized software and statistical tools as indicated. The data will be presented in the form of graphs/tables showing the change in scores over the 8 week treatment period.

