Safety Analyses: All adverse events will be coded using the Medical Dictionary for Regulatory Activities. Summaries will be presented for all adverse events, adverse events determined by the investigator to be related to study treatment, serious adverse events, and adverse events causing withdrawal from the study. Patient listings of serious adverse events and adverse events leading to withdrawal will be presented. Observed values and changes from baseline in laboratory results, vital signs and EKG parameters will be summarized descriptively. The use of concomitant medications will be monitored and will include all medications taken while the patient is treated with IMP.

Observed values in the C-SSRS will be monitored for all patients.

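### The SAP treats any score reduction as an indication that a larger study is feasible, but a score reduction is only a preliminary efficacy signal

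*SAP*

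**What the plan says.** The title presents the trial as "An Open Label, Proof-of-Principle, Pilot Study to Evaluate Pimavanserin". The SAP sets its outcome as follows: "The primary endpoint is the change in the Total Tic Score (TTS) of the Yale Global Tic Severity Scale (YGTSS) from baseline to week 8".

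The paragraph after the primary endpoint then gives the interpretation in two steps. The first sets the threshold: "Any degree of reduction in this score will be described as a suggestion of clinical benefit". The second draws the conclusion: "If there is suggestion of clinical benefit, we will consider this an indication of feasibility for a larger study". Between them the SAP extends the approach beyond the primary score: "A similar approach will be applied to the other scales mentioned in the study protocol".

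The Safety Analyses section provides for summaries of all, treatment-related and serious adverse events, and of those causing withdrawal. It adds: "Patient listings of serious adverse events and adverse events leading to withdrawal will be presented". Nothing in that section refers back to the feasibility conclusion.

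**The concern.** Whether scores fall and whether a larger trial can be run are different questions. The first concerns a possible treatment effect. The second concerns whether patients stay for the 8 weeks, tolerate the drug and supply scales that can be analysed. The SAP answers the second question with the answer to the first.

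What is at stake is the pilot's closing statement. Readers will look to a pilot for guidance on whether a larger study can be done. A report that follows the sentence as written could give an indication of feasibility because the score fell, even if retention was poor.

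**Working it through.** The SAP gives no sample size, expected change, standard deviation or retention figure, so there is no number to reproduce. The check is one of logic and needs no simulation.

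**Step 1: join the two sentences.** Any fall in score leads to a suggestion of clinical benefit ("Any degree of reduction in this score will be described as a suggestion of clinical benefit"). A suggestion of clinical benefit leads to an indication of feasibility ("If there is suggestion of clinical benefit, we will consider this an indication of feasibility for a larger study"). Together, any fall in score leads to an indication of feasibility.

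**Step 2: list what enters that chain and what does not.**

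| Question about a larger study | Information needed | Does it enter the chain? |
|---|---|---|
| Is there a hint of an effect? | Change in score, baseline to week 8 | Yes |
| Do patients complete 8 weeks? | Treated patients who reach week 8 | No |
| Is the drug tolerated? | Withdrawals for adverse events | No; summarised under Safety Analyses but not linked |
| Are the scales evaluable? | Treated patients with an evaluable week-8 YGTSS | No |

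The only input to the chain is the score change. The other three rows are what feasibility ordinarily means for a pilot.

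**Step 3: test the chain with two imagined pilots.** Suppose both report the same fall in score. In one, nearly all treated patients finish with evaluable scales. In the other, many leave early because of adverse events. Both meet the condition, so the sentence attaches the same indication of feasibility to each. It does not separate the two cases that a feasibility statement should separate.

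**Step 4: look for a sentence elsewhere that repairs it.** The Safety Analyses section would show the adverse-event withdrawals in the second pilot, so a reader of the full report could see the problem. No sentence in the SAP tells the author to take them into account when stating feasibility.

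**The case against.** The best defence is that the sentence is loosely worded rather than wrong. The trial is a proof-of-principle pilot, and its stated goal is to see whether the drug affects the score. In that setting, feasibility can be read as grounds for going further. The wording is hedged twice, as a suggestion and as an indication. Tolerability will be reported anyway, and the protocol may define feasibility properly.

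Most of this stands, and it limits the weight of the point. It does not remove it. If worth pursuing is what is meant, the word used still says something else. Any protocol criteria would sit beside the SAP's inference without making it valid.

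Three stronger readings are tempting, and the document does not support them:

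- **That the score is the sole feasibility criterion, or that the SAP ignores tolerability.** The sentence says if, not only if, and adverse-event withdrawals are both summarised and listed.
- **That patients who stop treatment are left out by design.** A reader might infer this from "If this score is reduced from baseline to week 8 while taking the study drug, this will suggest clinical benefit". The reference to taking the drug may only name the treatment period. The SAP does not say how patients who stop are handled, and the protocol may.
- **That dropout makes the rule easier to meet.** Outcome-related dropout could bias the score change in either direction, depending on who leaves. That is a separate question about the efficacy estimate, and rewording the feasibility sentence would not settle it.

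Nor is there a case here for rewriting the neighbouring sentences. Calling a fall a suggestion of clinical benefit is already tentative.

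**Conclusion.** The point holds in limited form: the SAP draws a feasibility conclusion from a preliminary efficacy signal that cannot carry it. The size is minor to moderate. Only the wording of the conclusion is affected; the endpoint, its estimate and the analysis set are untouched.

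This rests on two assumptions: that feasibility has its usual meaning for a pilot (completion, tolerability, evaluable data), and that the report follows the sentence as written. If the authors mean only that a larger study would be of interest, what remains is a misleading choice of word.

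**What to change.** Replace only the sentence that draws the feasibility conclusion, with:

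> A suggestion of clinical benefit will be reported as a preliminary efficacy signal that may support interest in a larger study. Feasibility will be described separately by the proportion of treated patients with an evaluable week-8 YGTSS and the proportion withdrawing for adverse events, each with an exact 95% CI, read with any criteria in the protocol.

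If only worth pursuing is meant, the smaller change is enough: in the same sentence, put *support for interest in* where the text now speaks of an indication of feasibility, and leave the rest as it is.

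The cost is one rewritten sentence and, in the fuller version, two descriptive proportions from data the SAP already plans to report or use. No new visit, measurement or threshold is needed. There are two downsides. The intervals will be wide: the SAP gives no sample size, but with assumed counts the exact (Clopper-Pearson) 95% interval is 35% to 93% for 7 of 10 evaluable and 46% to 88% for 14 of 20. The authors also give up a feasibility statement that follows from the score alone.
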